1.7.2. Screening Visit (day -60 to day -7)

If the participant is found to meet serology criteria (i.e. microneutralisation titre of <1:20, unless a decision is made by the study steering committee to specifically investigate individuals with higher MN titres), they will be invited for a screening visit. The screening visit will involve each participant attending the Imperial Clinical Respiratory Research Unit (ICRRU) at St Mary's Hospital, Paddington or Imperial Clinical Research Facility (ICRF) at Hammersmith Hospital for a past medical history review and medical examination to find out if they are suitable for the study. Potential subjects will be given a participant information sheet (PIS) detailing the study and experimental procedures. These will also be discussed with them by the study doctor or nurse. When the subject has had enough time to consider their participation in this study, ask any questions they may have, and only when they have agreed to take part will they be asked to read, sign and date a consent form in the presence of the study doctor or nurse who will also sign the consent form. Consent will be obtained prior to any history-taking, examination or tests are carried out. A copy will be kept in the research file, a copy given to the patient and a copy put into their medical notes.

A medical history will then be taken and clinical examination, lung function tests, chest X-ray, ECG and blood tests performed by the study team. Women of childbearing potential will be asked about current contraceptive use, and be required to use effective contraception (barrier, oral contraceptive pill, depot injection, implant, or total abstinence) throughout the study. Blood tests include general screening for underlying illness, specifically full blood count, urea and electrolytes, liver function tests, coagulation C-reactive protein, lymphocyte subsets, immunoglobulins, HIV, hepatitis B and C serology. A urine drug screen for illicit drugs and pregnancy test will also be performed, a positive result from either will result in the volunteer being excluded from the study.

These will all be done in the ICRRU at St Mary's Hospital or ICRF at Hammersmith Hospital. If the evaluation and the results of these tests show no evidence of infection or any other problems with the participants' health, and matches the inclusion / exclusion criteria then they will continue to the main part of the study.

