1.9. Exclusion criteria

Chronic respiratory disease (asthma, COPD, rhinitis, sinusitis) in adulthood

Inhaled bronchodilator or steroid use within the last 12 months

Use of any medication or other product (prescription or over-the-counter) for symptoms of rhinitis or nasal congestion within the last 3 months

Acute upper respiratory infection (URI or sinusitis) in the past 6 weeks

Smoking in the past 6 months OR >5 pack-year lifetime history

Subjects with allergic symptoms present at baseline

Clinically relevant abnormality on chest X-ray

Any ECG abnormality deemed clinically significant.

Those in close domestic contact (i.e. sharing a household with, caring for, or daily face to face contact) with children under 3 years, the elderly (>65 years), immunosuppressed persons, or those with chronic respiratory disease

Subjects with known or suspected immune deficiency

Receipt of systemic glucocorticoids (in a dose \geq 5 mg prednisone daily or equivalent) within one month, or any other cytotoxic or immunosuppressive drug within 6 months prior to challenge

Known IgA deficiency, immotile cilia syndrome, or Kartagener's syndrome

History of frequent nose bleeds

Any significant medical condition or prescribed drug deemed by the study doctor to make the participant unsuitable for the study

Pregnant or breastfeeding women

Positive urine drug screen

Detectable baseline antibody titres against influenza challenge strains

History of hypersensitivity to eggs, egg proteins, gentamicin, gelatin or arginine, or with life-threatening reactions to previous influenza vaccinations.

Participants may only be recruited if they have previously been involved in research if they have completed the earlier study and are beyond the washout period of any administered drugs or period of effect of any intervention that would cause interference for either study.

All women of childbearing age will have a **pregnancy test performed prior to virus inoculation** to exclude pregnancy and be required to use contraception **throughout the study**.

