If a participant loses capacity during the study, then the participant would be withdrawn from the study. Identifiable data or tissue already collected with consent would be retained and used in the study. No further data or tissue would be collected or any other research procedures carried out on or in relation to the participant.

The study is a low-risk non-CTIMP, carried out by an experienced PI and study team. The study has appropriate risk assessments in place and will be checked through the PRB system at ICRF.

Local monitoring will be carried out by study staff to ensure that CRFs are being completed, with no key data missing. Duke University will appoint one of their in house monitors to check the data produced, paper CRFs will be uploaded to their eCRF system. The monitor will check consent forms and data logs.

STATISTICS AND DATA ANALYSIS

Sample size estimation: the goal of this study is a proof-of-concept demonstration that physiological measures can detect influenza infection in the pre-symptomatic phase. As such, it is not possible to carry out a formal power analysis to determine the sample size, since no preliminary data on the effect size in influenza infection using the sensors in this study are available. However, heart rate variability (HRV) parameters have been shown to enable detection of sepsis with 86% sensitivity and 100% specificity in a study of 17 subjects (14 positive and 3 negative for sepsis)⁵. Therefore, we aim for a similar target for numbers of symptomatically infected individuals (13-15), which is likely to be achieved with a sample size of 20 subjects based on the previously established attack rate of 75% using this challenge virus. Larger studies would be required in the future to generate generalizable detection statistics, but the 20-subject sample size proposed here should be sufficient for concept demonstration.

Quantitative assessments of symptom scores, lung function, virus load, leukocyte numbers and inflammatory markers will be compared within subjects to determine differences between baseline and during infection. Intra-subject differences will be analysed using ANOVA and 2-tailed paired Student's t-tests or Wilcoxon signed rank test as appropriate. Correlations between inflammatory cell, illness severity, viral load and leukocyte counts will be examined using Spearman's rank correlations to investigate possible causal relationships.

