We aim to determine if the different sensors in the study can measure changes associated with influenza infection. For each sensor we will define and compute multiple metrics from the raw sensor output. Each of these metrics will be compared in the healthy versus sick states for each subject. We will consider a metric to be a potential predictor of illness in a single subject if there is a significant ($p < 0.05$) difference between the mean value in the sick and healthy state. Control comparisons will be made by computing the significance of differences between two different healthy periods (e.g. prior to infection and post recovery).

The potential predictors of illness from the within subject analysis will be compared across all subjects to determine if any sensor metrics provide generalizable indicators of illness. A metric will be considered a valid indicator if it is present in at least 85% of the within subject sick/healthy comparisons and less than 25% of the within subject control comparisons. This odds ratio is sufficient to achieve 80% power and a 5% error rate with a sample size of 13 subjects. Based on an established attack rate of 75% with this challenge virus, we estimate that will have 15 of our 20 subjects develop influenza. Therefore, the sample size of this study is sufficient to determine the feasibility of using the selected sensors to measure changes associated with influenza.

Data and all appropriate documentation will be stored for a minimum of 10 years after the completion of the study, including the follow-up period according to Imperial College London policy.

REGULATORY ISSUES

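### The stated 80% power and 5% error rate at 13 subjects belong to a significance test the plan does not name; at true rates of 85% and 25% the written rule passes a metric only about 23–34% of the time with 13–15 infected subjects

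*Combined protocol and SAP*

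**What the plan says.** All of this is in the Statistics and Data Analysis section, except the last point.

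- Each metric is tested within each subject at p < 0.05 for a "difference between the mean value in the sick and healthy state". The same test is applied as a control to two healthy periods in the same subject.
- Across subjects: "A metric will be considered a valid indicator if it is present in at least 85% of the within subject sick/healthy comparisons". A second condition in the same sentence requires the flag in under a quarter of the healthy-period controls.
- The next sentence gives the operating characteristics: "This odds ratio is sufficient to achieve 80% power and a 5% error rate with a sample size of 13 subjects". It names no test, no sidedness, and no true rates other than the two cut-offs.
- With a 75% attack rate the plan expects 15 of 20 volunteers to develop influenza, and concludes that the sample size is adequate for the feasibility question.
- The sample size paragraph just before says that "it is not possible to carry out a formal power analysis to determine the sample size". It justifies 20 volunteers by analogy with a 17-subject sepsis study and aims for 13–15 symptomatic infections.
- On who enters the denominator, section 1.7.2 sets a titre limit "unless a decision is made by the study steering committee to specifically investigate individuals with higher MN titres", while section 1.9 lists as an exclusion "Detectable baseline antibody titres against influenza challenge strains".

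**The concern.** A cut-off on an observed proportion and an assumed true proportion are different things. If a metric's true detection rate equals the cut-off, its observed rate falls below the cut-off a large part of the time, whatever the sample size. Power calculated for a test of 85% against 25% therefore says nothing about how often a metric will clear both cut-offs.

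This rule is the only explicit validity criterion for the primary objective, and the sufficiency conclusion leans on the quoted power. A reader would expect a metric that performs at the planning rates to be accepted four times in five, and would read a failed metric accordingly.

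**Working it through.** **Inputs.** From the plan: rates 0.85 and 0.25; 13 subjects (stated), 15 (expected infected), 14 (inside the 13–15 target); 80% power; 5% error. Assumed, because the plan is silent: the two comparisons are independent within a subject, and 85% and 25% are the true rates, being the only rates given. The implied odds ratio is (0.85/0.15)/(0.25/0.75) = 17.

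**Step 1: reproduce the plan's 13.** Two-sided 5% test of two proportions, 80% power, mean rate 0.55, difference 0.60:

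n = [1.96·√(2·0.55·0.45) + 0.842·√(0.85·0.15 + 0.25·0.75)]² / 0.60² = 9.52

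With continuity correction: (9.52/4)·[1 + √(1 + 4/(9.52·0.60))]² = 12.63, rounded up to **13**. Without the correction it is 10. For paired data, the exact two-sided McNemar test at n = 13, with discordant probabilities 0.85·0.75 and 0.15·0.25, has 78.2% power. So 13 is sound for a difference test.

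**Step 2: turn the written rule into counts.** At n = 13, 11/13 is 84.6% and fails, so the rule needs at least 12/13 sick flags and at most 3/13 control flags. At n = 14: at least 12 and at most 3. At n = 15: at least 13 and at most 3.

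**Step 3: pass probability at true rates 85% and 25%.** Exact binomial tails; the joint figure is the product under independence. Under any dependence the joint probability cannot exceed the smaller of the two.

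| n | Sick hurdle | Control hurdle | Joint, independent | Maximum, any dependence |
|---|---|---|---|---|
| 13 | 0.398 | 0.584 | 0.233 | 0.398 |
| 14 | 0.648 | 0.521 | 0.338 | 0.521 |
| 15 | 0.604 | 0.461 | 0.279 | 0.461 |

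Counting 11/13 as 85% gives 0.692 × 0.584 = 0.404 at n = 13.

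**Step 4: does a larger sample help?** No. The joint probability is 0.269 at n = 20 and 0.255 at n = 1000. Each hurdle tends to one half when the cut-off equals the true rate, so the product tends to 0.25.

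**Step 5: error rate.** If a metric has the same true rate in both comparisons, the probability of passing at n = 13 under independence is greatest near a common rate of 0.57, where it is 0.0001. With strong negative within-subject dependence it can reach about 0.003. Neither is 5%.

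**Step 6: better true rates.** Suppose the control rate is 5%, the nominal level of the within-subject test. The control hurdle is then passed with probability 0.997, 0.996 and 0.994 at n = 13, 14 and 15. Multiplying by the sick-hurdle tail:

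| True sick rate | n = 13 | n = 14 | n = 15 |
|---|---|---|---|
| 85% | 0.397 | 0.648 × 0.996 = 0.645 | 0.601 |
| 90% | 0.619 | 0.842 × 0.996 = 0.838 | 0.811 |
| 95% | 0.862 | 0.970 × 0.996 = 0.966 | 0.959 |

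**The case against.** *The 13 is a standard result.* It is, as step 1 shows, so this is not an arithmetic slip. What fails is attaching the figure to a rule it does not describe.

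*85% and 25% are minimum standards, and good metrics will beat them.* This has force. Any rule evaluated at its own boundary passes about a quarter of the time, and step 6 shows respectable pass rates for better metrics. But the plan assumes no better rates, and its power sentence is tied to these two numbers. The 5% control rate is itself an assumption, which autocorrelated sensor data could break.

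*The study is a proof of concept and disclaims a power analysis.* True, and 20 volunteers also rest on the sepsis analogy and the attack rate, so the sample size does not depend on this sentence alone. The sentence is still followed by a conclusion that the sample is sufficient.

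Three stronger readings are tempting and not supported:

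- *A metric truly at 85% usually fails the first hurdle.* That holds at n = 13 only. At 14 and 15 it passes with probability 65% and 60%.
- *The trial will probably reject its sensors wrongly.* The plan computes multiple metrics per sensor and asks whether any qualifies. As an illustration, seven independent metrics at 23.3% each give 1 − 0.767⁷ = 84% for at least one pass. Correlation lowers that, but the documents allow no verdict at sensor level.
- *The plan's test is McNemar's and should become the criterion.* No test is named, and exact McNemar gives 78%, not 80%, at 13. Alone it would also accept 6/13 against 0/13 (p = 2 × 0.5⁶ = 0.031), a metric that misses more than half of the sick subjects.

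**Conclusion.** The concern holds per metric. The 80% and 5% do not describe the 85%/25% rule. At those true rates, assuming independence within subject, the rule passes a metric with probability 23%, 34% and 28% at 13, 14 and 15 infected subjects. The ceilings of 40%, 52% and 46% need no independence assumption, so 80% is out of reach at these rates. The error rate is far below 5%; the 0.0001 figure rests on independence, equal true rates and n = 13. If true rates are better than the cut-offs the rule can perform well, but the plan does not say so.

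The power claim also conflicts with the plan's own statement that a formal power analysis cannot be done.

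Separately, sections 1.7.2 and 1.9 contradict each other on volunteers with detectable titres. A reader might infer a specific loss of infected subjects. The documents give neither the number of such volunteers nor their infection risk, so no figure is attached.

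**What to change.** Keep the 85%/25% rule and change the text around it.

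1. Delete "This odds ratio is sufficient to achieve 80% power and a 5% error rate with a sample size of 13 subjects".
2. In its place state the rule's operating characteristics per metric, with the independence assumption: about 23%, 34% and 28% at 13, 14 and 15 infected subjects for true rates of 85% and 25%. For an assumed 5% control rate, give about 40% (n = 13) and 60% (n = 15) at a true sick rate of 85%, 62% and 81% at 90%, and 86% and 96% at 95%. Pass rates do not rise steadily with n because the cut-offs fall on whole counts, so list each n.
3. Reword the conclusion that the sample size is sufficient so that it matches these figures, and reconcile it with the sample size paragraph's statement that no formal power analysis is possible.
4. Report observed sick and control rates for each metric with exact confidence intervals. An exact McNemar test may sit beside the rule but should not replace it; its 5% level would be per metric.
5. Reconcile sections 1.7.2 and 1.9 on detectable titres.

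The cost is a few sentences in the statistics section and one eligibility clarification. No volunteers or procedures are added. The price is a plainer statement that, at its own planning rates, the rule is a demanding one.

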1.23. Ethics approval

The Study Coordination Centre has obtained approval from the Fulham Research Ethics Committee (REC) and Health Regulator Authority (HRA). The study must also receive confirmation of capacity and capability from each participating NHS Trust before accepting participants into the study or any research activity is carried out. The study will be conducted in accordance with the recommendations for physicians involved in research on human subjects adopted by the 18th World Medical Assembly, Helsinki 1964 and later revisions.

1.24. Consent

Consent to enter the study will be sought from each participant only after a full explanation has been given, an information leaflet offered, time allowed for consideration, and any questions participants may have answered. Signed participant consent will be obtained prior to any screening tests being carried out. The right of the participant to refuse to participate without giving reasons must be respected. After the participant has entered the study the clinician remains free to give alternative treatment to that specified in the protocol at any stage if he/she feels it is in the participant's best interest, but the reasons for doing so should be recorded. In these cases the participants remain within the study for the purposes of follow-up and data analysis. All participants are free to withdraw at any time from the protocol treatment without giving reasons and without prejudicing further treatment.

1.25. Confidentiality

The Chief Investigator and all of the research team will preserve the confidentiality of participants taking part in the study and abide by the Data Protection Act. All personal/identifying information will be stored in password protected files, accessed via on password protected computer accounts. Only the study research nurses and doctors will have access to this information. PID (Personal Identifiable Data) will be stored for 10 years as per College retention policy. Paper medical records will be stored as per Trust policy, within a key-coded and fireproof door medical records storage facility within the ICRF. The site

file and paper CRFs will be kept in a locked filing cabinet, in a locked office within the Commonwealth building at Hammersmith campus.

The investigators will adhere to the GDPR and Imperial College London policies (UK Policy Frame Work for Health and Social Care Research) for handling any data.

Indemnity

Imperial College London as sponsor of this study holds negligent and non-negligent harm insurance policies which apply to this study.

Sponsor

Imperial College London will act as the main sponsor for this study. Delegated responsibilities will be assigned to the NHS trust taking part in this study. Sensor data analysis will be carried out by RTI International.

Funding

This study is funded by the United States Department of Defense DARPA via a collaboration with Duke University. They are acting as sole funders and this agreement is in place. The investigators will not receive any additional payment above their normal salaries. Participants in the study will have their travel costs refunded up to £20 per visit. They will also be given a donation of up to £2500 to compensate for the time and inconvenience of taking part in the study. These expenses will be paid at the end of the main study period, 28 days post-influenza inoculation. Where participants have completed the confinement period but fail to attend further follow-up appointments, they will be paid on a *pro rata* basis according to the number of visits they have attended.

1.26. Audits and inspections

The study may be subject to inspection and audit by Imperial College London under their remit as sponsor and other regulatory bodies to ensure adherence to GCP and the NHS Research Governance Framework for Health and Social Care (2nd edition).

1.29. Sample storage and usage

Samples of tissue, cells and fluids will be stored at the Commonwealth building and Medical School building sites at Imperial College London. Samples will be fully anonymised. These may be used for further assays or in other ethically approved studies. Samples and data may be shared with UK and international collaborators in studies that have been approved by local ethics committee and subject to a valid Materials Transfer Agreement. Data and samples sent outside the UK will be fully anonymised with no patient identifiable data transferred. As part of the current study, samples and associated clinical, immunological and virological data will be sent to collaborators at Duke University for transcriptomics, proteomics and metabolomics analysis.

STUDY MANAGEMENT

The day-to-day management of the study will be co-ordinated through [name], Clinical Senior Lecturer and Honorary Consultant in Infectious Diseases. In addition, a safety monitoring committee will convene monthly during the study to discuss all adverse events, protocol deviations, and other safety issues.

PUBLICATION POLICY

Our expectation is that after analysis the data from this study will be widely distributed in the medical and scientific community. Facilitated with presentations at local, national and international meetings, we hope to publish widely in the medical literature. In addition we have an excellent media department at Imperial College and will publicise research that has public interest when it is published. No identifying participant information will be published. The study will be registered on clinicaltrials.gov.

REFERENCES

1. Monto, A. S. Epidemiology of influenza. *Vaccine* **26 Suppl 4**, D45-48 (2008).
2. Pica, N. & Palese, P. Toward a Universal Influenza Virus Vaccine: Prospects and Challenges. *Annu. Rev. Med.* **64**, 189–202 (2013).
3. Günther, A. *et al.* Heart rate variability – a potential early marker of sub-acute post-stroke infections. *Acta Neurol. Scand.* **126**, 189–196 (2012).
5. Ahmad, S. *et al.* Continuous Multi-Parameter Heart Rate Variability Analysis heralds Onset of Sepsis in Adults. *PLoS ONE* **4**, e6642 (2009).
